**Coordinating Centre: Royal Infirmary Edinburgh**

## ABBREVIATIONS

AUC:	Area Under Curve
CAD:	Coronary Artery Disease
CI:	Confidence Interval
CVA:	Cerebrovascular Accident
CVD:	Cerebrovascular Disease
ECG:	Electrocardiogram
ESRF:	End stage renal failure
FEV1:	Forced Expiratory Volume (1 second)
Hb:	Haemoglobin
hsCRP:	Highly Sensitive C-Reactive Protein
HRQoL:	Health Related Quality of Life
IL:	Interleukin
IQR:	Interquartile Range
LV:	Left Ventricle
ICU:	Intensive Care Unit
MACE:	Major Adverse Cardiac Events
MALDI-MS:	Matrix Assisted Laser Desorption Ionization Mass Spectrometry
MI:	Myocardial Infarction
MINS:	Myocardial injury after non-cardiac surgery
POMS:	Postoperative morbidity survey
PVD:	Peripheral Vascular Disease
TIA:	Transient Ischaemic Attack
TnI, TnT:	Cardiac Troponin I, T
WHO:	World Health Organisation

## 1. Summary

### 1.1 Summary

Studies suggest that anaemia is associated with increased rates of complications and death following surgery. Some 2.1 million units of red blood cells are transfused each year in the UK, many in the perioperative period. Blood transfusion is an expensive and finite resource and optimum transfusion threshold in surgical patients is yet to be defined. Patients commonly receive blood transfusions to reduce the risk of myocardial ischaemia or improve perfusion of other organs (e.g. the kidneys), but this treatment may have important adverse effects including postoperative infection. There is great interest in restrictive transfusion practices (e.g. a transfusion trigger of 70 g L), however patients with co-existing cardiovascular disease have been excluded from studies of restrictive versus liberal transfusion strategies.

Uncertainty and the need for more evidence is highlighted in recent recommendations from the National Institute of Clinical Excellence (NICE) and the Association of Anaesthetists of Great Britain and Ireland (AAGBI). These recommend a restrictive transfusion practice, using 7g.dL as the “default” threshold, but both recommend caution for patients with CVD and NICE made further research in populations with CVD a research priority (1,2). We recently showed that meta-analysis of trial data restricted to populations with CVD (excluding cardiac surgery) indicate higher rates of acute coronary syndrome (ACS) with restrictive practice (RR: 1.78, 95% confidence interval 1.18 to 2.70, P=0.01; NNT ≈50), with substantial uncertainty remaining about mortality.(3) Uncertainty for patients with CVD is also supported by meta-analysis of trial data in cardiac surgery populations.(4) Hence, there is uncertainty if a “restrictive” perioperative transfusion strategy is optimal in the particular setting of cardiovascular disease.

Highly sensitive troponin assays are now available, which allow clinicians to reliably detect cardiac injury in increased numbers of patients who have undergone major surgery. Troponin release after surgery is common, as high as 40% in some studies. Many of these patients do not exhibit classical symptoms and signs of myocardial infarction (MI). Postoperative elevated troponin that does not fulfil standard definitions of MI is referred to as myocardial injury after non-cardiac surgery (MINS). Potential mechanisms for MINS are coronary events due to plaque rupture or coronary artery thrombosis, oxygen supply-demand imbalance or troponin leak resulting from inflammation.

Acute kidney injury (AKI) is also a leading cause of morbidity and mortality following major surgery with an estimated incidence of 10% in undergoing orthopedic surgery. Epidemiological work has identified anaemia as a risk factor for postoperative acute kidney injury (AKI).

Patients undergoing surgery for fractured neck of femur are often elderly, with co-morbidities and a high risk of postoperative complications, including MI and AKI. We propose to conduct a study with the following aims:

1. To describe the incidence of anaemia and transfusion in patients undergoing surgery for fractured neck of femur.
2. To use clinical and biochemical data to measure the incidence of perioperative cardiac and kidney injury in this group.
3. To evaluate highly sensitive serum troponin and urinary MALDI-MS as possible endpoints in a future prospective randomised trial of perioperative transfusion.

## **1.2 Lay Summary**

Many frail and elderly patients undergo surgery for hip fracture every year. Many of these patients have other health problems including heart disease and anaemia ("low blood count) either from chronic illness, bleeding at the time of injury or during subsequent surgery. Many patients will develop complications.

Doctors looking after these patients commonly prescribe a blood transfusion around the time of surgery, which may increase the amount of oxygen the blood can carry and therefore prevent heart attacks. It may also help patients get out of bed more quickly after surgery.

However, blood transfusions can have side effects such as causing heart failure or increasing infections after surgery. These can delay patient recovery too. Although some research has been done in this area, anaesthetists and surgeons are still unsure of when to prescribe blood transfusions to these patients. In particular, we are not sure about how low the blood count should be before a blood transfusion is ordered. Current guidelines suggest that prescribing at a lower haemoglobin count (70 g/L) is better, but there is research which suggests that this level is too low if the patient has a history of heart disease.

We wish to measure the incidence of anaemia, transfusion, heart attacks, kidney damage and other complications in patients undergoing surgery for fractured neck of femur. All patients that

present to our hospital with a broken hip will be able to take part in this study. We will measure heart damage with a blood test that is very sensitive and we will measure kidney damage with a standard blood test and a new urine test. We will also collect data on other complications. This will provide important information to design a future study looking at the correct transfusion level in the patients.

## 2. Background

### 2.1 Perioperative Blood Transfusion

Epidemiological studies suggest that patient co-morbidities, including anaemia, are associated with increased rates of complications and death following surgery. (5) Anaemia may reflect the severity of chronic disease, and may not have a causative relationship with poor outcomes. Despite this, patients commonly receive blood transfusions to increase haemoglobin concentration with the belief that this may improve clinical outcomes. Some 2.1 million units of red blood cells are transfused each year in the UK, many in the perioperative period, and blood transfusion is an expensive and finite resource. Evidence supports generally restrictive haemoglobin (Hb) transfusion triggers, but the optimum transfusion threshold for important sub-groups of surgical patients remains uncertain.

In the absence of major bleeding, perioperative red blood cell transfusions are typically given to improve oxygen delivery to organs and tissues. Clinicians have particular concern about the risk of myocardial ischaemia, especially among patients with cardiovascular disease. Decision-making is also influenced by potential adverse effects ranging from fluid overload to immune-mediated outcomes, such as increased postoperative infection(6) and tumour recurrence.(7) Published research comparing restrictive and liberal transfusion strategies have typically compared a transfusion threshold of 7-8 g.dL with 9-10 g. dL.(8) Many of these trials excluded patients with co-existing cardiovascular disease (CVD) and those that included this population typically used less restrictive transfusion triggers (usually  $\geq 8\text{g. dL}^{-1}$ ). This reflects concerns over precipitating or exacerbating major adverse cardiac events (MACE) by exposing patients with CVD to anaemia.

### 2.2. Fractured Neck of Femur

Patients undergoing surgery for fractured neck of femur (NOF) are an ideal population in which to improve evidence for transfusion practice in populations with CVD. First, they are carried out in large numbers (over 65 000 in the year 2015) in a high proportion of NHS

hospitals.(9) Second, patients are typically high risk, elderly, and have co-existing disease including CVD. Third, as this population is elderly there is a high prevalence of pre-existing anaemia, the major risk factor for perioperative blood transfusion. Fourth, fracture-and surgery-associated bleeding result in a high incidence of acute anaemia and high transfusion rates.(10) Finally, there is a high incidence of perioperative mortality, complications (including cardiac complications) and high health/social care resource utilisation, which might be attributable in part to anaemia/transfusion management. In a recent Cochrane review specifically investigating red blood cell transfusion practice in people undergoing surgery for hip fracture, we found low quality evidence in relation to mortality, functional recovery or postoperative morbidity between 'liberal' versus 'restrictive' thresholds.(11) This review included the FOCUS trial, a large clinical trial of restrictive versus liberal transfusion strategy in patients with fractured NOF.(12) Factors limiting the wider applicability of this trial included: the use of a transfusion threshold of 8g.dL (or "symptomatic") in the restrictive group, a short period of exposure to anaemia, and the use of a composite primary outcome with a focus on rehabilitation (death or inability to walk at 60 days) rather than informing care in the perioperative period. This trial used clinical reporting of cardiac events and noted a trend to higher rates in the restrictive group (RR 1.65 (95% CI: 0.99 to 2.74)).

### **2.3 Measurement of myocardial injury.**

Troponin is a protein released from myocardial tissue following myocardial damage. In combination with clinical information and electrocardiography it is used routinely to diagnose and rule out myocardial infarction (MI)(13). Modern Troponin assays are able to detect myocardial necrosis with a high degree of precision. There are two measurable cardiac troponins, Troponin T (TnT) and I (TnI). High sensitivity assays have enabled detection of Troponin in non-Acute Coronary Syndrome (ACS) states such as sepsis, pulmonary embolus, anaemia, critical illness (14) and following surgery where it also correlates strongly with outcome. The VISION Group measured postoperative troponin in a large cohort of patients aged 45yrs or older and found that troponin was an independent predictor of 30d mortality. Importantly, isolated elevations in Tn without symptoms or other clinical signs had similar associations with mortality as MI which fulfilled universal definition. Authors defined Myocardial Necrosis After Non-cardiac Surgery (MINS) as "prognostically relevant elevated Troponin within 30 days of non-cardiac surgery which does not fulfil universal definitions for MI". ECG evidence of ischaemia is not necessary for diagnosis. (15). Other studies have demonstrated a high incidence of elevated postoperative troponin level in general surgical

settings, (16–19) in vascular surgery (20,21) and in orthopaedic surgery (22,23). Potential mechanisms for the elevation in troponin seen following surgery include coronary plaque rupture and thrombosis (Type I MI), and oxygen supply/demand imbalance (Type II MI) and possible cellular “leak” due to inflammation. There is uncertainty whether troponin elevation following surgery reflects true myocardial necrosis or is an “inflammation-mediated” phenomenon.(17) Similarly, it is not known whether the association with adverse outcomes is an epiphomenon, or whether biologically plausible interventions that may decrease myocardial injury can improve patient outcomes. Available evidence strongly supports the hypothesis that more liberal transfusions in “at risk” populations with CVD could reduce Type II MI, which might reduce cardiovascular complications and improve clinical outcomes.(3)

#### **2.4 Measurement of kidney injury.**

Current definitions of AKI rely on elevation of serum creatinine, however this typically occurs late in the evolution of renal injury. Currently both the RIFLE and Acute Kidney Injury Network (AKIN) systems exist to classify Acute Kidney Injury.(24) Development of clinically useful early biomarkers of AKI remains elusive. There is an established need for new biomarkers enabling a more accurate and timely detection of acute kidney injury. (25)

Matrix Assisted Laser Desorption Ionization Mass Spectrometry (MALDI-MS) is a novel predictive test of kidney injury which uses urine electrophoresis coupled to a mass spectrometer. Preliminary studies suggest this technique could detect AKI five days earlier than existing biomarkers. Until recently it was a highly specialised research tool, not suitable for clinical practice. However, an early predictive test for AKI based on the analysis of urinary peptide biomarkers by MALDI-MS has now been developed. Such a platform could be for point-of-care detection of AKI in the postoperative setting.

#### **2.5 Current research strategy in this area.**

Uncertainty and the need for more evidence is highlighted in recent recommendations from the National Institute of Clinical Excellence (NICE) and the Association of Anaesthetists of Great Britain and Ireland (AAGBI). These recommend a restrictive transfusion practice, using 7g.dL as the “default” threshold, but both recommend caution for patients with CVD and NICE made further research in populations with CVD a research priority (1,2). We recently showed that meta-analysis of trial data restricted to populations with CVD (excluding cardiac surgery) indicate higher rates of acute coronary syndrome (ACS) with restrictive practice (RR: 1.78, 95% confidence interval 1.18 to 2.70, P=0.01; NNT ≈50), with substantial uncertainty remaining about mortality.(3) Uncertainty for patients with CVD is also supported by meta-

analysis of trial data in cardiac surgery populations.(4) Hence, there is uncertainty if a “restrictive” perioperative transfusion strategy is optimal in the particular setting of cardiovascular disease.

Consistent with prioritisation by NICE(1) and the NIHR specialty networks (NIHR haematology specialty group HTA priority 2013; topic 20239), we believe that a large randomised trial of transfusion thresholds in a population with high prevalence of CVD and perioperative complications is warranted. Patients undergoing surgery for fractured neck of femur are ideal for such a study. We intend to seek funding for a feasibility study that will lead to an application for a large UK-wide trial (on behalf of the NIAA), which will progress a “precision medicine” approach to the clinical and cost-effective use of blood transfusions. Data provided by this study will be vital to inform such a study.

## **2.6 Involvement of patients.**

A recent research prioritisation exercise was conducted in the field of perioperative medicine by James Lind Alliance partners which included both patients and carers. This identified improving outcomes for patients undergoing emergency surgical care and for elderly patients undergoing surgery as being in the top 10 research questions for this field. Our proposed study fulfils aspects of both these questions.

## **3 Study Objectives and Experimental Design**

### **3.1 Study Objectives**

The objectives of this study is threefold:

1. to measure the incidence of perioperative anaemia and transfusion in patients undergoing surgery for fractured neck of femur.
2. to understand the changes that occur over time in the level of Troponin I in patients undergoing surgery for fractured neck of femur and to answer whether Troponin I can be used in these patients as a real-time marker of myocardial injury. We hope that this will validate the use of Troponin I as the endpoint for a future trial looking at the impact of liberal vs restrictive perioperative blood transfusion in this patient group.
3. to measure the incidence of acute kidney injury in patients undergoing surgery for fractured neck of femur and to evaluate the performance of MALDI-MS against conventional tests of renal function.

### 3.2 PICO Design

Study design was developed using “Patient Intervention Comparator Outcome” (PICO) method.

**Population:** We will recruit 200 adult patients undergoing emergency surgery for fractured neck of femur, aged over 50 years.

**Intervention:** We will use blood samples taken preoperatively and at 24 and 72 hours by the research team or (where able) leftover serum from routinely collected blood samples to minimise need for venepuncture in these patients. We will perform an ECG on the third postoperative day. Urine will be collected at 2 time points post-operatively (within 24 hours and 4-6 days post-operatively).

**Comparator:** This is an exploratory study in which we are trying to understand the dynamics of serum Troponin I, serum creatinine and urinary MALDI-MS following surgery. We will compare patterns of cardiac and renal injury in anaemic and non-anaemic patients.

#### **Outcome:**

*Primary:* Myocardial injury (based on hsTroponin>Upper reference limit [URL]);

*Secondary:* Acute Kidney Injury (KDIGO Stage); Urinary MALDI-MS

#### *Other clinical outcomes:*

Acute Coronary syndrome (using universal definition)

Mortality (30; 90 days)

POMS score

Infectious complications

Incidence of delirium

Hospital length of stay

Unplanned hospital readmission within 90 days

Health Related Quality of Life (HRQoL) at 90 days (Using “EQ-5D” questionnaire)

Secondary care costs during 90 days post-randomisation

## 4. Study Objectives

### 4.1 Objectives

#### 4.1.1 Primary Objective

- To determine prospectively the dynamic changes in Troponin I in patients undergoing surgery for fractured neck of femur

#### 4.1.2 Secondary Objectives

- To estimate the rate of acute kidney injury using Acute Kidney Injury Network (AKIN) Classification, Serum Creatinine and Urinary MALDI-MS.
- To observe whether changes in Troponin I levels are reflected by electrocardiographic changes via an ECG taken on the 3rd postoperative day.
- To define the clinical diagnosis rate of myocardial infarction according to universal definitions
- To observe rate of transfusion and transfusion trigger
- To estimate the incidence of postoperative complications, in particular infectious complications and delirium.
- To measure hospital length of stay
- To measure 30-day, 90-day and hospital mortality.
- To measure economic and quality of life outcomes

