## 5. Study Design

This will be a prospective cohort study. Patients will be consented and then enrolled in the study within 48 hours of hospital admission with fractured neck of femur. Over the intra- and postoperative period, we will collect baseline demographic data, and daily information regarding myocardial infarction, postoperative complications (including death) and blood transfusion.

We will take blood samples for markers of renal and kidney injury preoperatively and at 24 hours and 72 hours following surgery. We will record the results of blood tests that have been routinely taken. Patients will have a point-of-care haemoglobin measurement immediately following surgery in recovery using the “haemocue” system. Urine will be collected at 2 time points post-operatively (within 24 hours and 4-6 days post-operatively).

We will perform a postoperative ECG 72 hours following surgery. We will collect clinical data on postoperative morbidity score (POMS) on day 7, on infectious and cardiac complications prior to hospital discharge. We will also collect economic and quality of life data for up to 90 days following surgery.

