### 6.1 Recruitment Rate

The trauma and orthopaedic unit at the Royal Infirmary of Edinburgh perform over 1000 procedures for fractured neck of femur per year and 98% undergo surgical fixation. Based on

published data(12) and UK audit data we expect ≈60% (N = 600) of patients to have cardiovascular co-morbidity. Assuming a recruitment rate of 50%, 300 patients would be potentially recruited in 12 months (7 per week). Assuming a “worst case scenario” of 30% recruitment, we expect to recruit ≈200 patients over 12 months.

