### *Preoperative Data*

At baseline the following information will be collected:

- date of admission
- Demographic information
- Type of surgery proposed
- Cardiovascular risk factors
- Cardiac medications
- Charleson Comorbidity Index
- Preoperative haemoglobin (Hb)
- Preoperative serum TnI
- Preoperative Creatinine

- Preoperative Urinary MALDI-MS

*Intraoperative Data*

- Date of surgery
- Type of anaesthesia
- Duration of surgery
- Lowest intraoperative Haematocrit (Hct) or Hb measured
- Hb immediately after surgery
- Number of units blood transfused
- Postoperative analgesia
- Postoperative destination (e.g. Ward, Critical Care Unit)

*Postoperative Data*

First 72 hours postop

- Serum TnI and Creatinine, Hb, urinary MALDI-MS within 24 hours and 4-6 days postoperatively. Where possible blood samples will be timed with existing blood sampling.
- ECG on the 3rd postoperative day
- Transfusion requirement
- Relevant clinical information major adverse cardiac events (MACE) including myocardial infarction.

Hospital Discharge/30 days

- Transfusion requirement
- Length of hospital stay
- MACE
- POMS
- Incidence of Delirium
- Infectious complications
- Mortality 30 days

90 Days

- Emergency readmission
- Mortality
- HRQoL
- Secondary care costs

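### The plan relates troponin change to ECG change but collects one postoperative ECG and no earlier one, so new ECG findings cannot be separated from old

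*Combined protocol and SAP*

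**What the plan says.** Section 4.1.2 lists, among the secondary objectives, "To observe whether changes in Troponin I levels are reflected by electrocardiographic changes via an ECG taken on the" third postoperative day.

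The ECG is scheduled in three other places, each time as one postoperative recording:

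- Section 3.2 (PICO Design): "We will perform an ECG on the third postoperative day".
- Section 5 (Study Design): "We will perform a postoperative ECG 72 hours following surgery".
- Section 8 (Data Collection), under the first 72 hours after surgery: "ECG on the 3 rd postoperative day".

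The preoperative list in section 8 includes "Preoperative serum TnI" along with haemoglobin, creatinine, urinary MALDI-MS, cardiovascular risk factors and cardiac medications. It has no ECG. On routine results, section 5 states "We will record the results of blood tests that have been routinely taken", which does not cover ECGs. Section 11.2 has no ECG analysis.

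On background risk, section 6.1 states "we expect ≈60% (N = 600) of patients to have cardiovascular co-morbidity".

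**The concern.** The objective sets two changes against each other. One side, troponin I, has a preoperative value and later values. The other side has one tracing. A single tracing shows what is present on day 3 and not when it appeared.

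In an elderly group with much cardiovascular disease, some day-3 abnormalities will have been there before the fracture. If they are mixed with new ones, the observed link with troponin change can go wrong in either direction. It is diluted if old abnormalities are unrelated to the troponin change. It is inflated if earlier heart disease raises both the chance of an abnormal ECG and the troponin response. The data collected would not show which had happened.

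**Working it through.** **Document check.** There is no plan figure to reproduce, so the first step is to set the two sides of the objective next to each other.

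| | Troponin I | ECG |
|---|---|---|
| Preoperative value in section 8 | yes | none |
| Postoperative value | yes, more than one | one, day 3 |
| Routine earlier results to be recorded (section 5) | blood tests | not mentioned |
| Rule for telling new from old | preoperative value available | none given |

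A change on the ECG side cannot be derived from this data set. That conclusion uses no assumed number. The flow chart in Appendix A is not shown in the text available for this check and could not be read.

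**Illustration of size.** The documents give neither the prevalence of old ECG abnormality nor the incidence of new change. Both are assumed here:

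- q = share of patients with an old abnormality, 10-50%.
- i = share who develop a new change, 5-20%, taken as independent of q.
- N = 200, the planned sample (section 11.1).
- Old abnormalities are taken to be still visible on day 3.

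Proportion with an abnormal day-3 ECG: q + (1 - q)i.

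Share of those abnormal ECGs with no new change: q(1 - i) / [q + (1 - q)i].

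- q = 0.10, i = 0.20: abnormal = 0.10 + 0.90 × 0.20 = 0.28, or 56 of 200. No new change: 0.10 × 0.80 / 0.28 = 0.29.
- q = 0.30, i = 0.10: abnormal = 0.30 + 0.70 × 0.10 = 0.37, or 74 of 200. No new change: 0.30 × 0.90 / 0.37 = 0.73. True new changes expected: 200 × 0.10 = 20.
- q = 0.50, i = 0.05: abnormal = 0.50 + 0.50 × 0.05 = 0.525, or 105 of 200. No new change: 0.50 × 0.95 / 0.525 = 0.90.

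Share with no new change over the whole grid:

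| Old abnormality q | i = 5% | i = 10% | i = 20% |
|---|---|---|---|
| 10% | 0.66 | 0.47 | 0.29 |
| 20% | 0.79 | 0.64 | 0.44 |
| 30% | 0.85 | 0.73 | 0.55 |
| 40% | 0.88 | 0.78 | 0.62 |
| 50% | 0.90 | 0.82 | 0.67 |

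**Effect on a comparison.** Suppose old abnormality is equally common in patients with and without a troponin rise, and new change occurs in i₁ and i₀ of them. The difference in the proportion abnormal on day 3 is [q + (1 - q)i₁] - [q + (1 - q)i₀] = (1 - q)(i₁ - i₀). The true difference is multiplied by 1 - q: by 0.9 at q = 10% and by 0.5 at q = 50%. If old abnormality is more common in those with a troponin rise, this shrinkage no longer applies and the bias can run the other way.

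**The case against.** Several points count against a strong version of this concern.

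- **The wording may be loose.** ECG changes can mean ischaemic findings on the day-3 tracing and not a before-and-after difference. On that reading the objective can be answered, and only the wording needs attention. The paired reading is equally natural, because the same sentence speaks of changes in troponin and troponin does have a baseline. The text should say which is meant.
- **No reading rule is given.** A reader might infer that old abnormalities will be counted as perioperative change. The documents do not say how the tracing will be read, so they support only that old and new cannot be separated and that old findings could be counted.
- **Admission ECGs may exist.** They may, but no section says they will be retrieved. The record access in section 10 is for cardiac events and mortality.
- **The size is assumed.** The 60% is a figure for cardiovascular co-morbidity, not for ECG abnormality. A simpler formula, q / [q + (1 - q)i], gives 71-95% for q of 20-50% and i of 5-10%, and a reader might prefer that narrow, high range. It treats every patient with an old abnormality as unable to develop a new one. Allowing new change in them at the same rate gives 64-90% on the same inputs. If they are at higher risk, the share falls further: with q = 0.30 and new change in 20% of them but 10% of the rest, it is 0.30 × 0.80 / 0.37 = 0.65 instead of 0.73.
- **Infarction and MINS.** A reader might infer that the split between infarction and myocardial injury is compromised. That is possible but not shown. Infarction also draws on daily information (section 5), clinical data on cardiac events (section 8) and record review (section 10). Section 2.3 notes that MINS does not require ECG evidence of ischaemia.
- **The study is exploratory.** This explains the absence of a power calculation. It does not supply a comparator for a stated objective.

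**Conclusion.** The point holds: the planned data contain no ECG comparator, so the objective, read as change against change, cannot be met from what the protocol collects. This rests on the schedule and data list alone.

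The size is uncertain. The 29-90% range depends on the assumed inputs and on independence of old and new findings; it shows that the problem could be modest or dominant, and it is not an estimate for this cohort.

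The consequence is contained. The ECG is not among the endpoints in section 4.2, this is one of eight secondary objectives, and the primary troponin endpoint keeps its preoperative value. Minor to moderate, and worth correcting because the remedy is cheap.

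**What to change.** 1. In section 8, add to the preoperative data a field for any ECG already in the notes from admission or earlier, with its date.
2. State that day-3 findings are classed against it as new, old or unknown, and by whom; preferably the reader does not see the troponin results.
3. In section 11.2, relate only new findings to troponin change, and report the number classed as unknown.
4. In section 4.1.2, say that where no comparator exists the result is described as the association with ECG abnormality present on day 3, not with change.

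The cost is one data field, the time to read the earlier tracing, and a few lines of text. No extra ECG or patient contact is needed. The downside is that some patients will be unknown. The documents do not say how many usable earlier ECGs there will be, so the yield cannot be predicted. If it proves low, the reworded objective in step 4 still stands and can be answered with the single day-3 ECG.
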